9.4. Subject identification

The subjects will be identified by their screening number (SCXXX) and their randomisation number (RDXXXX) at W0 in order to maintain their data confidentiality.

The format of the screening number consists in letters SC followed by 3 digits; the 3 digits start from 001 and are given to the subjects in a chronological order during the screening in each study centre.

The format of the randomisation number consists in letters RD followed by 4 digits (the 1st digit corresponds to the number of the study centre); this number will be assigned to the subjects in the order of inclusion at W0 in each study centre as follow:

Intertek: from n° RD1001 to RD1100

CHU Nantes: from RD2001 to RD2100

The subject numbers will be documented in the CRF.

Subjects will be identified to the Sponsor only by their subject numbers, date of birth and gender. All subjects included in the study will be listed in the study status table.

9.5. Randomization and blinding

In order to minimise the bias, the study will be conducted in double blind and randomized conditions.

9.5.1. Description of randomisation/blinding measures

Prior to the start of the study, a randomisation list will be drawn up by SYLIA-STAT LANCRENON to be transmitted to the clinical packaging organisations for labelling.

The labels of the product materials identify only the randomisation number.

Subjects who fulfils all criteria will be randomized at each study centre in 1:1 way to receive:

- The dermo-cosmetic product (fla 688977 33)
- The standard moisturizer

The first IP will be dispensed to the subjects in the chronological order of their inclusion in the study at the visit 1, and no number should be omitted or skipped. This number will be documented in the CRF.

9.5.2. Maintenance of randomisation codes and procedures for breaking codes

SYLIA-STAT LANCRENON will send codes to the study centres.

The randomisation code (contains in sealed envelopes) identifies the IP provided/administered to each subject, throughout the period of the study. The investigator may only open this envelope if needed following a SAE, i.e only if the circumstances of this SAE require knowledge of the product which has been applied. In this event the investigator will inform the Sponsor. The investigator should mark on the code envelope the reason for the envelope being opened, the date of opening and should sign the envelope. On request, all code envelopes will be returned to the Sponsor at the end of the study.

The randomisation code will be also broken after the database lock and with agreement from the Sponsor.

9.6. Screen failures, subject withdrawals and replacement criteria

Non-included subjects, that is, subjects who have signed informed consent but are removed from the study during the screening process because they do not meet the inclusion/exclusion criteria, are classed as screen failures. Subjects who leave the study after randomisation or assignment to study treatment are classed as withdrawals rather than screen failures, even if the subject had not started the study treatment.

Subjects not completing the study for any reason will be considered as withdrawals and will not be replaced.

Criteria for withdrawal:

1. Subject withdraws consent: subjects will be free to withdraw from the study at any time and for any reason. (In accordance with the Declaration of Helsinki),
2. Adverse event / Serious adverse event: any adverse event that the investigator considers it is not in the subject's best interest to continue,
3. Protocol deviation (after agreement of the Sponsor and/or the investigator),
4. Subject lost to follow-up,
5. Other reasons: other reasons than stated above which requires subject to be withdrawn as:
 - any other situation where, in the opinion of the investigator, continuation of the study would not be in the interest of the subject;
 - Discontinuation of the study by the Sponsor.

The CRF should be completed up to the time of screen failure or withdrawal.

A subject will be considered as "Lost to Follow-up" after 3 phone calls (recorded) and a mail (registered mail with Acknowledgement of receipt) stayed without answer.

All subjects who are prematurely discontinued from the study should have the reason carefully documented by the Investigator/study team in the CRF, final page 'End of study', and, as applicable, on the Adverse Event Form and/or Concomitant Treatment Form.

No follow-up will be planned for the withdrawn subjects.

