| Return of IP and daily log | | X | X | X |
| Compliance, Health and Concomitant medication checks | X | X | X | X |
| Cosmetic acceptability and efficacy questionnaires | | | | X |
| Products overall tolerance appreciation by the Dermatologist and the subject | | | | X |
| Adverse Events | X | X | X | X |
| Complete CRF, final page 'End of study' ⁽⁶⁾ | | | | X |

⁽¹⁾ Visit flexibility = ± 3 days

⁽²⁾ Details of relevant medical or surgical history experienced over the subject's life time, including any allergies or sensitivities, may include physical examination.

⁽³⁾ Details any medication taken in the 4 weeks prior to Visit 1.

⁽⁴⁾ IP application made at home until the day before the visits.

⁽⁵⁾ Completed after each IP application.

⁽⁶⁾ At Final Visit, if subject completes study as planned, or at any time before that in case of withdrawal.

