11.4. Prior and concomitant medication

Any topical or systemic therapy used in the 4 weeks prior the Visit 1 will be recorded in the CRF, with the following information:

- name of the drug, type of formulation, and unit strength,
- dose administered,
- start and stop dates,
- reason for treatment.

The following treatments are not allowed:

- isotretinoin treatment within the 6 months prior the Visit 1 and during the study
- surgical/medical procedures on the face (deep cleansing, dermabrasion, peeling, light-therapy, laser...) during the study,
- systemic drugs for more than 3 consecutive days related to antibiotics, anti-inflammatory, corticoids, anti-acneic in the 4 weeks prior the Visit 1 and during the study,
- topical drugs for more than 3 consecutive days related to antibiotics, anti-inflammatory, corticoids, anti-acneic in the 2 weeks prior the Visit 1 and during the study,

Any subject using a concomitant therapy during the study that could interfere with the assessment of the IP will be considered for withdrawal from the study, at the discretion of the investigator.

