- Minor i.e. not serious
- Serious

CAUSAL RELATIONSHIP of the event to the use of the IP will be according to the investigator's clinical judgement and described by the terms:

- Not related The event is clearly related to other factors such as the subject's clinical state, therapeutic interventions, or concomitant medications administered to the subject or no IP has been used (where applicable)
- Unlikely The event was most likely produced by other factors such as the subject's clinical state, therapeutic interventions, or concomitant medications administered to the subject; and do not follow a known response pattern to the IP.
- Possible The event follows a reasonable temporal sequence from the time of IP administration; and/or follows a known response pattern to the study treatment; but could have been produced by other factors such as the subject's clinical state, therapeutic interventions, or concomitant medications administered to the subject.
- Probable The event follows a reasonable temporal sequence from the time of IP administration; and follows a known response pattern to the IP; and cannot be reasonably explained by other factors such as the subject's clinical state, therapeutic interventions, or concomitant medications administered to the subject.
- Definite As for Probable AND either occurs immediately following IP administration, or improves on stopping the IP, or reappears on repeat exposure, or there is a positive reaction at the specific application site.
- Unknown There is insufficient information to make a judgment

ACTION WITH RESPECT TO IP will be described by the terms:

- None
- Discontinue product (the subject continues on the study, if the protocol allows it, with or without re-introduction of the IP)
- Adjust dosage if the protocol allows it
- Withdraw from study

CORRECTIVE TREATMENT to be reported as a concomitant medication.

- None
- Medication
- Non-medication therapy

FREQUENCY of the event

- Isolated
- Intermittent
- Constant

SEVERITY of the event will be described in terms of mild, moderate or severe according to the investigator's clinical judgement.

- Mild: Did not interfere with normal everyday activities
- Moderate: Interfered to some extent with everyday activities
- Severe: Was not tolerated and interfered with normal everyday activities

EXPECTED / UNEXPECTED will be described by the terms:

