- Expected AE conforms with known AEs associated with the IP as described in the supporting literature (i.e. Investigator Brochure)
- Unexpected

IMMEDIATE OUTCOME and FOLLOW UP OUTCOME of the event will be described by the terms:

- Ongoing
- Resolved
- Stabilized / discharged
- Lost to follow up (except for immediate outcome)

During the subject's study participation, all adverse events should be followed up to determine the final outcome. When an AE persists at the end of the subject's participation in the study, follow-up will be required for those adverse events classified as "possible", "probable" or "definite" related to the IP.

Follow-up should continue until

- the event has resolved or,
- the event is considered to be stabilized (at discretion of investigator and/or Sponsor) or,
- the subject has been discharged to the care of their own physician

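### Section 9.6 permits discretionary withdrawal from the study for adverse events or deviations, plans no exit lesion count, and leaves open whether a subject may stop a product and stay

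*Combined protocol and SAP*

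**What the plan says.** Section 9.6 lists the grounds for withdrawal from the study. Criterion 2 begins "Adverse event / Serious adverse event: any adverse event that the investigator considers" and goes on to require a judgement that continuing is against the subject's best interest. Criterion 3 is "Protocol deviation (after agreement of the Sponsor and/or the investigator". Section 11.4 adds that a subject on a therapy "that could interfere with the assessment of the IP will be considered for withdrawal from the study, at the discretion of the investigator". None of the three is automatic.

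After withdrawal, 9.6 says "The CRF should be completed up to the time of screen failure or withdrawal" and "No follow-up will be planned for the withdrawn subjects". In the flow chart (Section 4), footnote 6 attaches only the end-of-study CRF page to an early exit: "if subject completes study as planned, or at any time before that in case of withdrawal". Lesion counts are scheduled at W0, W4, W8 and W12 and at no exit visit.

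Section 11.7.1.2 separates stopping product from leaving in one place, an action code on the adverse event form: "Discontinue product (the subject continues on the study, if the protocol allows it, with or without re-introduction of the IP". No section in the available text says whether the protocol does allow it. The same section keeps some safety follow-up after the end of participation ("follow-up will be required for those adverse events classified as" possible, probable or definite), but this yields no lesion counts.

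Section 14.2 analyses efficacy in the per-protocol set only, with major deviations defined at the blind review. Its ITT set is for safety and requires at least one application of each product. Section 14.3 makes the W12 total lesion count the primary contrast, from a mixed model over visits.

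**The concern.** Section 6 expects the test product to change both the acne and the tolerance of the drug. Intolerance, recourse to other acne therapy and deviations are therefore plausible reasons for leaving that could differ by arm. If they do, and if leavers differ from stayers in ways that baseline and earlier visits do not explain, the W12 contrast is shifted.

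Three features make this harder to repair. A W12 count that was never taken cannot be restored when the analysis plan is written. A subject who leaves before W4 has no post-baseline count at all. And if the reason for leaving is later classed as a major deviation, that subject's W4 and W8 counts also drop out of the efficacy analysis. With the stop-and-stay question unsettled, the two centres may also handle the same event differently.

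**Working it through.** **1. The plan's own figure.** Inputs from 14.1: difference 1.15, SD 5.0, R² 0.70, two-sided 5%, power 80%, drop-out 10%.

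n per arm = 2 × (5.0 × (1.960 + 0.842) / 1.15)² × (1 − 0.70) = 296.74 × 0.30 = 89.02, rounded up to 90. Then 180 / 0.90 = 200. The stated size reproduces.

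**2. Precision.** SE = √(2 × 25 × 0.30 / n) = 0.4082 at 90, 0.3974 at 95 and 0.3873 at 100 per arm. The residual SD given baseline is 5 × √0.30 = 2.74. Power = Φ(difference / SE − 1.96). At 90 per arm this is 80.4% for 1.15, 73.0% for 1.05 and 54.9% for 0.85.

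**3. Assumptions.** The documents give no loss by arm or by reason and no prognosis for leavers, so everything here is assumed. Half of the planned 10% loss is taken as recoverable by the change (5% on average), split 3% v 7% or 2% v 8%. Leavers would have ended 2.5 lesions (0.9 residual SD) or 5 lesions (1.8 residual SD) worse than stayers.

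**4. Shift in the W12 contrast.** If W4 and W8 do not show the excess, or are dropped with the subject, shift = excess × difference in loss:
- 2.5 × 0.04 = 0.10 (9% of 1.15)
- 5 × 0.06 = 0.30 (26% of 1.15)

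If W4 and W8 are kept and show the excess in full, the mixed model recovers part of it. This was computed by generalised least squares on the pattern means, with product-by-visit means, compound symmetry, and half of leavers going after W4 and half after W8. Power, in brackets, is for heavier loss on control.

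| Assumed loss; excess | Not shown or dropped | Shown, correlation 0.3 | 0.5 | 0.7 |
|---|---|---|---|---|
| 3% v 7%; 2.5 lesions | 0.10 (73.0%) | 0.062 (76.0%) | 0.041 (77.5%) | 0.024 (78.8%) |
| 2% v 8%; 5 lesions | 0.30 (54.9%) | 0.185 (65.7%) | 0.124 (71.0%) | 0.071 (75.3%) |

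If leaving is spread over the three intervals and the excess builds up (one third at W4, two thirds at W8), the shifts for correlations 0.3 to 0.7 are 0.088 to 0.078 and 0.265 to 0.233. Raising total loss to 8% v 12% or 7% v 13% changes the tabulated shifts by less than 0.01.

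**5. Direction.** With leavers worse than stayers, heavier loss on control flatters control and costs power. Heavier loss on test flatters test. With no true effect, false superiority is then 1 − Φ(1.96 − shift / 0.408): 4.3% for 0.10 and 11.0% for 0.30, against 2.5%. Equal loss with equal prognosis gives no shift.

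**6. What the remedy costs in power.** Counts from subjects with no product effect dilute the difference: 1.15 × 0.95 = 1.0925 and 1.15 × 0.90 = 1.035.

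| Subjects with no product effect | 100 per arm | 95 per arm (half of drop-out recovered) |
|---|---|---|
| none | 84.4% | 82.5% |
| 5% | 80.5% | 78.5% |
| 10% | 76.2% | 74.0% |

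**The case against.** A reader might infer that any adverse event or deviation forces a subject out. The text does not support that. Criterion 2 carries a best-interest test, criterion 3 needs agreement, and 11.4 says only that withdrawal will be considered. Section 10.5 also sets a compliance floor of 75% for the drug, so up to 21 of 84 evening applications can be missed within the threshold, and departures from the regimen are to be documented in the report. Short breaks for irritation are thus accommodated, and the adverse event form already distinguishes stopping from leaving. All of this stands. It leaves permanent discontinuation unsettled, and it does not supply an exit count.

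The mixed model uses W4 and W8 counts, which can shrink the shift considerably. That also stands, provided that the subject stays in the per-protocol set and the earlier visits reflect the later course.

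The strongest objection concerns the remedy. Counts recovered after a product stop or interfering therapy could still be excluded from the per-protocol set at blind review, so the power losses above would remain in the analysis for which they were computed. This is right. The gain lies only in an all-randomised analysis. On power alone the exchange is roughly neutral (76% to 79% in the milder retained-data case, against 74% to 78% at 95 per arm with 5% to 10% dilution), so the argument is about bias. The all-randomised analysis also answers a somewhat different question from a primary objective framed around combined use over 12 weeks of application, which is a reason to report both.

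**Conclusion.** The point holds as a design weakness that should be corrected, with medium confidence. As written, the plan can lose or discard W12 counts for reasons connected with the products, and it has no all-randomised efficacy analysis to set against the per-protocol result. The 10% inflation protects numbers, not comparability.

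The size and direction of any bias are unknown. The shifts of 0.02 to 0.30 lesions illustrate what assumed imbalances would do and are not estimates for this trial. The upper end needs a 2% v 8% imbalance, a 1.8 SD excess and uninformative or discarded earlier visits.

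A reader might infer that the plan favours the test product. The documents do not support that. Section 6 predicts better tolerance on the test product, which would point to heavier loss on control and a shift against the test product. It also describes a keratolytic that promotes desquamation, and scaling is a scored tolerance sign in 11.6.2.3, which could point the other way.

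One limit on the reading is that the content of Appendix 4 (the drug's product characteristics) is not in the available text, so the statement about the missing permission covers the sections that are.

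**What to change.** - **Sections 9.6 and 11.4:** state that a subject may stop one or both products and remain in the study. Such subjects keep the remaining scheduled visits with lesion counts, unless consent is withdrawn, attendance is against the subject's interest, or the pregnancy rule in 11.7.1.1 applies. This also settles the condition in the 11.7.1.2 action code.
- **Section 9.6:** replace the no-follow-up sentence with lesion counts and GEA at the last attendance, where possible.
- **Section 14.2:** add a W12 efficacy analysis of all randomised subjects, using all collected counts including those after a product stop or interfering therapy. Report it with the per-protocol analysis, and do not claim superiority from the per-protocol result alone if the two disagree. State that the recovered counts protect the all-randomised analysis and not the per-protocol contrast.

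The cost is protocol wording, one added analysis, and written ethics committee approval if made as a substantial amendment (16.2, 16.6). The visits are already scheduled: at most 20 × 3 = 60 attendances if every planned drop-out were recovered, or 30 if half were. Withdrawn consent and loss to follow-up are not recoverable. The downside is a few off-product visits and some dilution of the all-randomised effect, as tabulated above. The visit and exit-count changes need to be in place before subjects start leaving.

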10. INVESTIGATIONAL PRODUCTS

10.1. Description

Sponsor should supply the investigators with the following cosmetic products.

- Studied product: fla 688977 33
- Comparative product: Hydréane légère, Cosmétique Active International (on the market)

The Investigator's brochure will confirm the safety of the studied product for use in this study. It will state that the IP to be tested do not entail any serious foreseeable risk for the health of the subjects taking part in the study as long as the conditions specified in the protocol are followed. It will be sent to CPP for protocol submission.

The comparative product (Hydréane légère) is already on the market (cf Appendix 3 for informations).

The fixed combination of "Adapalene 0.1% / benzoyl peroxide 2.5% treatment" will be the marketed pharmaceutical drug Epiduo® 0.1%/2.5% gel; Galderma Laboratoires, as tube of 30g (cf Appendix 4). Investigators will provide the treatment in its branded packaging funded by the Sponsor.

10.2. Packaging and labelling

The IP (cosmetic products) will be packed and labelled by the Sponsor, separately for each subject as per the randomization, according to the French requirements.

The container labels will have the following information in French:

| | |
|------------------------|----------------------------|
| ➤ Study reference | Référence de l'essai |
| ➤ Product type | Type de produit |
| ➤ Randomisation number | Numéro de randomisation |
| ➤ Expiry date | Date de péremption |
| ➤ Storage conditions | Conditions de conservation |
| ➤ Precautions for use | Précautions d'emploi |

INTERDIT A LA REVENTE
A N'UTILISER QUE DANS LE CADRE ET POUR LA DUREE DU TEST

10.3. Storage conditions

The IP (cosmetic products) will be stored at ambient temperature in a secure limited access area of each study centre.

The subjects will be asked to store the IP at home at ambient temperature.

The IP (marketed pharmaceutical drug) will be stored at temperature not exceeding 25°C in a secure limited access area of each study centre. The subjects will be asked to store the IP at home at a temperature not exceeding 25°C.

10.4. Dosage and application of the IP

At W0, W4 and W8, subjects will be supplied with 1 tube of Epiduo® and 1 of the 2 cosmetic products according to the randomisation for a 4-week application period.

Once-a-day, on the morning, the subjects will apply about one hazelnut of IP (amount equivalent to the amount generally used for a product of this type) to their face (avoiding eyes contour) in place of their usual product.

Once-a-day, on the evening (before bedtime), the subjects will apply the IP “Adapalene 0.1%/ benzoyl peroxide 2.5% treatment” on their face (affected area) on a cleansed and dried skin. The product must be applied in thin layer evenly with fingertips, avoiding eyes, lips and nostrils.

The subjects will have to wash carefully their hands after each application.

All IP applications will be made at home from W0 until the day before the last visit (W12) (i.e. 12-week application period).

10.5. IP accountability, compliance and destruction

Receipt, checking, registration of storage and dispensing of the IP will be carried out in each study centre.

The subjects will record each IP (cosmetic product & drug) application in their daily log. Their compliance with this requirement will be checked by a member of the study team at each visit from a review of the daily log. The number of IP applications will be reported in the CRF in order to compute the compliance at each visit as follow:

Compliance will be expressed by the ratio of the number of applications of the IP actually applied to the theoretical number of IP applications.

The compliance of the cosmetic products should be comprised between 80-120% whereas the compliance of the drug treatment should not be inferior to 75%.

Any deviation from the required IP use regime will be documented in the study report.

At the end of the study, the used and unused IP (cosmetic products) will be checked and then returned to the Sponsor whereas the unused IP (marketed pharmaceutical drug) will be destroyed by each study centre.

11. STUDY ASSESSMENTS AND CONDUCT

11.1. General

The study will be conducted under ambulatory conditions. All the assessments will be carried out at the study centres.

No study procedures will be carried out before the subject and/or legal representatives (for minor subjects) has/have given written informed consent.

